8.4.2 Day 0: Enrolment and vaccination visit

Volunteers will not be considered enrolled in the study until they have received a vaccine. Before vaccination, the eligibility of the volunteer will be reviewed. Pulse, blood pressure and temperature will be observed and if necessary, a medical history and physical examination may be undertaken to determine need to postpone vaccination depending on criteria listed in section 7.3.5. Vaccinations will be administered as described below.

8.4.2.1 Vaccination

Before each vaccination, the on-going eligibility of the volunteer will be reviewed. The vaccines will be administered intramuscularly into the deltoid of the non-dominant arm (preferentially), according to the relevant SOP. The injection site will be covered with a sterile dressing and the volunteer will stay in the CCVTM for 60 minutes (± 10 minutes) after

CONFIDENTIAL

vaccination, in case of immediate adverse events. Observations will be taken 30 minutes (± 10 minutes) after vaccination and the sterile dressing removed and injection site inspected.

After vaccination the following procedures will be undertaken:

Volunteers will be given an oral thermometer, tape measure and diary card (paper or electronic), with instructions on use, along with the emergency 24 hour telephone number to contact the on-call study physician if needed. Volunteers will be instructed on how to self-assess the severity of these AEs. There will also be space on the diary card to self-document unsolicited AEs, and whether medication was taken to relieve the symptoms. Diary cards will collect information on the timing and severity of the following solicited AEs:

Local solicited AEs	Systemic solicited AEs
Pain	Fever
Redness	Feverishness/Chills
Warmth	Joint pains
Itch	Muscle pains
	Fatigue
	Headache
	Malaise
	Nausea

Table 3. Solicited AEs as collected on post vaccination diary cards

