5.1.1 Primary Outcome Measures

The specific endpoints for safety and reactogenicity will be actively and passively collected data on adverse events

The following parameters will be assessed for the study group

- Occurrence of solicited local reactogenicity signs and symptoms for 7 days following the vaccination
- Occurrence of solicited systemic reactogenicity signs and symptoms for 7 days following the vaccination
- Occurrence of unsolicited adverse events for 28 days following the vaccination
- Change from baseline for safety laboratory measures
- Occurrence of serious adverse events during the whole study duration

Volunteers will undergo clinical follow up for adverse events for 28 days following completion of the vaccination regimen. SAEs will be collected throughout the study. The duration of follow up reflects the desire to obtain safety data with the first use of MVA-NP+M1 manufactured on the AGE1.CR.pIX avian cell line.

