9.2.6 Suspected Unexpected Serious Adverse Reaction (SUSAR)

A serious adverse reaction, the nature and severity of which is not consistent with the information about the medicinal product in question set out in the IB.

9.3 Foreseeable Adverse Reactions:

The foreseeable ARs following vaccination with MVA NP+M1 include injection site pain, erythema, warmth, swelling, pruritus, myalgia, arthralgia, headache, fatigue, fever, feverishness, malaise, nausea, muscular and articular pain.

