9.7 Assessment of severity

The severity of clinical and laboratory adverse events will be assessed according to the scales in Table 6 -Table 8.

CONFIDENTIAL

Adverse Event	Grade	Intensity
Erythema at injection site*	1	>3 - ≤50 mm
	2	>50 - ≤100 mm
	3	>100 mm
Swelling at injection site	1	>3 - ≤20 mm
	2	>20 - ≤50 mm
	3	>50 mm
Ulceration/necrosis of skin at injection site	1	-
	2	-
	3	Any

Table 6. Severity grading criteria for local adverse events

*erythema or swelling ≤3mm is an expected consequence of skin puncture and will therefore not be considered an adverse event.

Table 7. Severity grading criteria for physical observations.	

	Grade 1 (mild)	Grade 2 (moderate)	Grade 3 (severe)
Fever (oral)	37.6°C - 38.0°C	38.1°C – 39.0°C	>39.0°C
Tachycardia (bpm)*	101 - 115	116 - 130	>130
Bradycardia (bpm)**	50 – 54	40 - 49	<40
Systolic hypertension (mmHg)	141 - 159	160 - 179	≥180
Systolic hypotension (mmHg)***	85 - 89	80 - 84	<80
Diastolic hypertension (mmHg)	91 - 99	100 - 109	≥110

*Taken after ≥10 minutes at rest

**Use clinical judgement when characterising bradycardia among some healthy subject populations, for example, conditioned athletes.

***Only if symptomatic (e.g. dizzy/ light-headed)

GRADE 0	None: Symptom not experienced	
GRADE 1	Mild: Short-lived or mild symptoms; medication may be required. No limitation to usual activity	
GRADE 2	Moderate: Mild to moderate limitation in usual activity. Medication may be required.	
GRADE 3	Severe: Considerable limitation in activity. Medication or medical attention required.	

Table 8. Severity grading criteria for local and systemic AEs.

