9.10 Safety Holding Rules

Safety holding rules have been developed considering the fact this is the first time the MVA-NP+M1 vaccine, developed on the novel immortalised duck retinal cell line AGE1.CR.pIX, is used. 'Solicited adverse events' are those listed as foreseeable adverse events in section 9 of the protocol, occurring within the first 7 days after vaccination (day of vaccination and six subsequent days). 'Unsolicited adverse events' are adverse events other than the foreseeable AEs occurring within the first 7 days or any AEs occurring after 7 days post vaccination.

The group holding rules are as follows:

- Solicited local adverse events: If 2 or more volunteers present the same Grade 3 solicited local adverse event beginning within 2 days after vaccination (day of vaccination and one subsequent day) and persisting at Grade 3 for >48 hrs
- Solicited systemic adverse events: If 2 or more volunteers present the same Grade 3 solicited systemic adverse event beginning within 2 days after vaccination (day of vaccination and one subsequent day) and persisting at Grade 3 for >48hrs.
- Unsolicited adverse events: If 2 or more volunteers develop the same Grade 3 unsolicited adverse event (including the same laboratory adverse event) that is considered possibly, probably or definitely related to vaccination and persists at Grade 3 for >48hrs.
- A life-threatening reaction considered possibly, probably or definitely related to vaccination occurs
- A serious adverse event considered possibly, probably or definitely related to vaccination occurs

• Death considered possibly, probably or definitely related to vaccination

If a volunteer has an acute illness (moderate or severe illness with or without fever) or a fever (oral temperature greater than 37.5°C) at the scheduled time of administration of investigational product, the volunteer will not receive the vaccine at that time. The vaccine may be administered to that volunteer at a later date within the time window specified in the protocol (see Table 4) or they may be withdrawn from the study at the discretion of the Investigator.

If a holding rule has been met and following an internal safety review it is deemed appropriate to restart dosing, a request to restart dosing with pertinent data must be submitted to the regulatory authority as a request for a substantial amendment. The internal safety review will consider:

- The relationship of the AE or SAE to the vaccine.

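### Injection-site swelling is solicited under sections 9.3 and 9.10 and graded in mm, but it is the only foreseeable local reaction missing from the Table 3 diary list

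*Protocol*

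**What the plan says.** Four parts of the protocol bear on this.

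- **Diary (section 8.4.2.1).** "Diary cards will collect information on the timing and severity of the following solicited AEs". The list that follows, captioned "Table 3. Solicited AEs as collected on post vaccination diary cards", has four local items: pain, redness, warmth and itch. The card also has free space for unsolicited events, and volunteers receive a tape measure.
- **Foreseeable reactions (section 9.3).** The list reads "injection site pain, erythema, warmth, swelling, pruritus, myalgia, arthralgia, headache, fatigue, fever, feverishness, malaise, nausea". Section 4.5 also names swelling among the expected local effects.
- **Holding rules (section 9.10).** Solicited events "are those listed as foreseeable adverse events in section 9 of the protocol", within the first 7 days. The solicited local rule is met when two or more volunteers have the same Grade 3 event, with onset on day 0 or day 1, lasting more than 48 hours at Grade 3.
- **Grading (section 9.7, Table 6).** "Swelling at injection site" has its own scale: Grade 1 above 3 and up to 20 mm, Grade 2 above 20 and up to 50 mm, Grade 3 above 50 mm.

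The primary outcomes in section 5.1.1 include "Occurrence of solicited local reactogenicity signs and symptoms for 7 days following the vaccination". Section 10 adds that frequency, severity and duration of adverse events will be presented.

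**The concern.** The protocol carries two solicited lists that differ by one local reaction. Sections 9.3 and 9.10 count swelling as solicited; the instrument that gathers solicited events day by day does not ask about it. Two things are at stake. Swelling contributes to a primary outcome, yet it would be ascertained by a weaker method than the four reactions beside it. It can also trigger a holding rule defined by onset day and duration, which are the two facts a daily diary entry supplies.

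**Working it through.** No sample-size, power or event-rate figure is involved. The check is a comparison of lists, followed by a comparison of the holding rule with the visit schedule.

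**1. Lists**

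| Section 9.3 (local) | Table 3 (diary) | Size scale in Table 6 |
|---|---|---|
| Pain | Pain | No |
| Erythema | Redness | Yes |
| Warmth | Warmth | No |
| Swelling | Absent | Yes |
| Pruritus | Itch | No |

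Four of five match. The systemic items of 9.3 (myalgia, arthralgia, headache, fatigue, fever, feverishness, malaise, nausea) all have a counterpart in Table 3. Swelling is therefore the only 9.3 reaction with no diary row.

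**2. Other routes of capture**

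- Section 8.4.2.1: the injection site is inspected about 30 minutes after vaccination.
- Section 8.4.3 and Table 4: adverse events are recorded at every follow-up visit without condition. Only the history and physical examination row is marked as done if considered necessary.
- Section 9.6: local events observed or reported over 28 days are recorded.

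Swelling can therefore be recorded. What is missing is the daily prompt.

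**3. Holding rule against the visits**

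Let *t* be the onset in hours after vaccination and *D* the time spent at Grade 3. The rule requires onset on day 0 or 1, so *t* < 48, and *D* > 48. Hence *t* + *D* > 48.

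- Day-2 visit at the nominal 48 h: *t* < 48 < *t* + *D*, so every qualifying swelling is present.
- Day-2 visit at 24 h (early edge of the window): not yet present if *t* > 24. Illustration: *t* = 30, *D* = 50, present from 30 to 80 h.
- Day-2 visit at 72 h (late edge): already below Grade 3 if *t* + *D* < 72. Illustration: *t* = 6, *D* = 50, present from 6 to 56 h.
- Day-7 visit: the earliest is day 5, or 120 h. A swelling with *D* just over 48 h has ended by about 48 + 48 = 96 h. Both illustrations end before 120 h.

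A qualifying swelling that lasts only just over 48 h is thus seen at Grade 3 at one visit at most, and at none in the two off-nominal illustrations. One sighting shows the grade at that moment. It establishes neither the onset day nor persistence beyond 48 h; those must come from recall or free text.

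**4. Which rule applies**

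| | Solicited local rule | Unsolicited rule |
|---|---|---|
| Onset limit | Day 0 or 1 | None |
| Causality | Not required | Possibly, probably or definitely related |
| Persistence at Grade 3 | More than 48 h | More than 48 h |

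Swelling is solicited by the 9.10 definition. By Table 3 it is not, and a volunteer who writes it down must use the space for unsolicited events. The two rules can give different answers for the same event.

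**5. Size for the primary outcome**

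With 6 volunteers, one missed case changes the observed frequency of swelling by 1/6 = 16.7 percentage points. The proportion with any local reaction changes by that amount only if swelling was the volunteer's sole local reaction.

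**The case against.** The strongest reply is that little would be lost. Staff assess local events at days 2 and 7, and a swelling that meets the holding rule is necessarily present at a visit held at 48 hours. Once recorded, section 9.10 has events followed to resolution or stabilisation, so duration can be pursued. That section classifies by event and timing, not by where the event was written, so early swelling is solicited even if it appears as free text. Section 5.1.1 includes unsolicited events too, so recorded swelling reaches a primary outcome under either label. The study is descriptive, has six volunteers, and is reviewed after the first three.

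Most of this stands, and it rules out some stronger readings. A reader might infer that swelling is not actively collected, that volunteers are never asked about it, or that the holding rule cannot be evaluated for it. Unconditional adverse-event recording at each visit and the 48-hour argument contradict all three. Nor does the gap of about 2 to 8 days between the day-2 and day-7 visits (day 3 to 5 at the shortest, day 1 to 9 at the longest) measure a hole in the rule: at the nominal schedule, a swelling that starts in that gap is past the rule's onset limit.

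The reply does not supply a daily record. Onset day and continuous time at Grade 3 would be reconstructed afterwards for this one reaction, and the visit window allows the day-2 visit to fall where a qualifying swelling is not visible. Nor does the reply explain why a reaction with its own mm scale is left off the card.

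**Conclusion.** The inconsistency is real and needs correcting. Swelling is one of five foreseeable local reactions and the only one without a daily prompt, so its 7-day occurrence may be under-ascertained relative to the other four. Its onset and its persistence beyond 48 hours at Grade 3 would rest on recall or free text, most of all when the day-2 visit is held near 24 or 72 hours. It is also unclear in operation which of two holding rules with different onset and causality conditions would be applied. The loss is one of precision and comparability; neither the primary outcome nor the holding rule fails outright.

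This assumes that Table 3 is complete as published and that the diary card, which is not part of the protocol text, follows it. A later analysis plan could settle the label but could not recover daily measurements that were never requested.

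**What to change.** Reconcile Table 3 with sections 9.3 and 9.10 so that one solicited list applies to the diary, the primary outcome and the holding rules. Add a swelling row in mm to Table 3 and to the diary card, measured daily over the 7-day solicited period. The same edit can align minor wording, such as the combined feverishness and chills item in Table 3 against feverishness alone in 9.3. No holding-rule threshold needs to change.

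The cost is one table row and one extra diary line for volunteers to complete. The tape measure is already issued, and no visits or staff are added. The change should be made before the first vaccination.

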8.4.2.2 Sequence of Enrolment and Vaccination of Volunteers

The first volunteer will be vaccinated alone and the profile of adverse events assessed. No other volunteers will be vaccinated until at least 48 hours have elapsed following the first volunteer being vaccinated. The CI and the LSM will be asked to provide the decision on whether to proceed after the review of the first volunteer. Provided no serious adverse reactions have occurred then a further two volunteers will be vaccinated at least 1 hour apart from each other. An independent safety review will be carried out by the LSM after the first 3 volunteers in the group have been vaccinated. This review will include the results of safety blood tests at day 7 post vaccination. The CI and the LSM will be asked to provide the decision on whether to proceed with vaccination of the remaining 3 volunteers.

8.4.3 Subsequent visits: days 2, 7, 21 and 28.

Follow-up visits will take place 48 hours (\pm 24h), 7 days (\pm 2 days), 21 days (\pm 2 days) and 28 days (\pm 2 days) after vaccination. Volunteers will be assessed for local and systemic adverse events, interim history, physical examination, review of diary cards (paper or electronic) and

blood tests at these time points as detailed in the schedule of attendances. Blood will also be taken for exploratory immunology.

If volunteers experience adverse events (laboratory or clinical), which the investigator (physician), CI and/or LSM determine necessary for further close observation, the volunteer may be admitted to an NHS hospital for observation and further medical management under the care of the Consultant on call.

Attendance number	1 ^s	2	3	4	5	6
Timeline (days)	<90	0	2	7	21	28
(weeks)		0		1	3	4
Time window (days)			±1	±2	±2	±2
Informed consent	Х					
Review contraindications,						
inclusion and exclusion	Х	Х				
criteria						
Medical history, physical	х	(X)	(X)	(X)	(X)	(X)
examination	~	(//)	(//)	(//)	(//)	(//)
Vital signs^	Х	Х	Х	Х	Х	Х
Vaccination		Х				
Diary card provided		Х				
Diary card collected						Х
Record adverse events			Х	Х	Х	Х
Biochemistry ^{\$} /	5	5	5	5		5
Haematology (mL)	5	5	5	5		5
Urinalysis (protein, glucose,	х					
blood)	^					
Urinary b-HCG (women only)	Х	Х				
HBsAg, HCV Ab, HIV serology	5					
(mL)	5					
Exploratory immunology [£]		50		50	50	
Blood volume per visit	10	55	5	55	50	5
Cumulative blood volume**	10	65	70	125	175	180

Table 4. Schedule of visits for volunteers

 s^{s} = screening visit; (X) = if considered necessary ^ = Vital signs includes pulse, blood pressure and temperature; s^{s} = Biochemistry will include Sodium, Potassium, Urea, Creatinine, Albumin and Liver function tests. t^{e} = Exploratory Immunology will include IFN- γ T cell ELISPOT and further experimental assays to be confirmed at a later date. ** Cumulative blood volume for volunteers if bloods taken as per schedule, and excluding any repeat safety blood test that may be necessary.

9 ASSESSMENT OF SAFETY

Safety will be assessed by the frequency, incidence and nature of adverse events and serious adverse events arising during the study.

9.1 Interim Safety Reviews

Interim safety reviews with the Chair of the LSC (LSM) are planned after the first three volunteers, prior to vaccination of the remaining recruited volunteers. Safety reviews consist of an assessment of the profile and severity of adverse events reported and will include the results of safety blood tests at day 7 post vaccination. Interim safety data may also be made available to manufacturers (in coded format) as specified in the contract with the manufacturer(s).

9.2 Definitions

9.2.1 Adverse Event (AE)

An AE is any untoward medical occurrence in a volunteer, which may occur during or after administration of an Investigational Medicinal Product (IMP) and does not necessarily have a causal relationship with the intervention. An AE can therefore be any unfavourable and unintended sign (including an abnormal laboratory finding), symptom or disease temporally associated with the study intervention, whether or not considered related to the study intervention.

9.2.2 Adverse Reaction (AR)

An AR is any untoward or unintended response to an IMP. This means that a causal relationship between the IMP and an AE is at least a reasonable possibility, i.e., the relationship cannot be ruled out. All cases judged by the reporting medical Investigator as having a reasonable suspected causal relationship to an IMP (i.e. possibly, probably or definitely related to an IMP) will qualify as adverse reactions.

9.2.3 Unexpected Adverse Reaction

An adverse reaction, the nature or severity of which is not consistent with the applicable product information (e.g. IB for an unapproved IMP).

9.2.4 Serious Adverse Event (SAE)

A SAE is an AE that results in any of the following outcomes, whether or not considered related to the study intervention.

- Death
- Life-threatening event (i.e., the volunteer was, in the view of the Investigator, at immediate risk of death from the event that occurred). This does not include an AE that, if it occurred in a more severe form, might have caused death.
- Persistent or significant disability or incapacity (i.e., substantial disruption of one's ability to carry out normal life functions).
- Hospitalisation, regardless of length of stay, even if it is a precautionary measure for continued observation. Hospitalisation (including inpatient or outpatient hospitalisation for an elective procedure) for a pre-existing condition that has not worsened unexpectedly does not constitute a serious AE.
- An important medical event (that may not cause death, be life threatening, or require hospitalisation) that may, based upon appropriate medical judgment, jeopardise the volunteer and/or require medical or surgical intervention to prevent one of the outcomes listed above. Examples of such medical events include allergic reaction requiring intensive treatment in an emergency room or clinic, blood dyscrasias, or convulsions that do not result in inpatient hospitalisation.
- Congenital anomaly or birth defect.

9.2.5 Serious Adverse Reaction (SAR)

An adverse event (expected or unexpected) that is both serious and, in the opinion of the reporting Investigator or Sponsors, believed to be possibly, probably or definitely due to an IMP or any other study treatments, based on the information provided.

9.2.6 Suspected Unexpected Serious Adverse Reaction (SUSAR)

A serious adverse reaction, the nature and severity of which is not consistent with the information about the medicinal product in question set out in the IB.

9.3 Foreseeable Adverse Reactions:

The foreseeable ARs following vaccination with MVA NP+M1 include injection site pain, erythema, warmth, swelling, pruritus, myalgia, arthralgia, headache, fatigue, fever, feverishness, malaise, nausea, muscular and articular pain.

9.4 Expected Serious Adverse Events

No serious adverse events are expected in this study.

9.5 Causality Assessment

For every AE, an assessment of the relationship of the event to the administration of the vaccine will be undertaken by the CI-delegated clinician. An intervention-related AE refers to an AE for which there is a probable or definite relationship to administration of a vaccine. An interpretation of the causal relationship of the intervention to the AE in question will be made, based on the type of event; the relationship of the event to the time of vaccine administration; and the known biology of the vaccine therapy (Table 5). Alternative causes of the AE, such as the natural history of pre-existing medical conditions, concomitant therapy, other risk factors and the temporal relationship of the event to vaccination will be considered and investigated. Causality assessment will take place during planned safety reviews, interim analyses (e.g. if a holding or stopping rule is activated) and at the final safety analysis, except for SAEs, which should be assigned by the reporting investigator.

CONFIDENTIAL

0No RelationshipNo temporal relationship to study product and Alternate aetiology (clinical state, environmental or oth interventions); and Does not follow known pattern of response to study product1UnlikelyUnlikely temporal relationship to study product and Alternate aetiology likely (clinical state, environmental or oth interventions) and Does not follow known typical or plausible pattern of response study product.2PossibleReasonable temporal relationship to study product; or Event not readily produced by clinical state, environmental other interventions; or Similar pattern of response to that seen with other vaccines3ProbableReasonable temporal relationship to study product; and
interventions); and Does not follow known pattern of response to study product1UnlikelyUnlikelyUnlikely temporal relationship to study product and Alternate aetiology likely (clinical state, environmental or oth interventions) and Does not follow known typical or plausible pattern of response study product.2PossibleReasonable temporal relationship to study product; or Event not readily produced by clinical state, environmental other interventions; or Similar pattern of response to that seen with other vaccines
1 Unlikely Unlikely temporal relationship to study product and 1 Alternate aetiology likely (clinical state, environmental or oth interventions) and Does not follow known typical or plausible pattern of response study product. 2 Possible Reasonable temporal relationship to study product; or Event not readily produced by clinical state, environmental other interventions; or Similar pattern of response to that seen with other vaccines
Alternate aetiology likely (clinical state, environmental or oth interventions) and Does not follow known typical or plausible pattern of response study product. Possible Reasonable temporal relationship to study product; or Event not readily produced by clinical state, environmental other interventions; or Similar pattern of response to that seen with other vaccines
interventions) and Does not follow known typical or plausible pattern of response study product. Possible Reasonable temporal relationship to study product; or Event not readily produced by clinical state, environmental other interventions; or Similar pattern of response to that seen with other vaccines
2 Possible Reasonable temporal relationship to study product; or Event not readily produced by clinical state, environmental other interventions; or Similar pattern of response to that seen with other vaccines
Event not readily produced by clinical state, environmental other interventions; or Similar pattern of response to that seen with other vaccines
other interventions; or Similar pattern of response to that seen with other vaccines
3 Probable Reasonable temporal relationship to study product; and
Event not readily produced by clinical state, environment, other interventions or
Known pattern of response seen with other vaccines
4 Definite Reasonable temporal relationship to study product; and
Event not readily produced by clinical state, environment, other interventions; and
Known pattern of response seen with other vaccines

Table 5. Guidelines for assessing the relationship of vaccine administration to an AE.

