9.6.1 Reporting Procedures for Serious AEs

In order to comply with current regulations on serious adverse event reporting to regulatory authorities, the event will be documented accurately and notification deadlines respected. SAEs will be reported on the SAE forms to members of the study team immediately the Investigators become aware of their occurrence, as described in relevant safety reporting SOPs. Copies of all reports will be forwarded for review to the Chief Investigator (as the Sponsor's representative) within 24 hours of the Investigator being aware of the suspected SAE. The local safety monitor (LSM) will be notified of SAEs that are deemed possibly, probably or definitely related to study interventions; the LSM will be notified immediately (within 24 hours) of the Investigators' being aware of their occurrence. SAEs will not normally be reported immediately to the ethical committee(s) unless there is a clinically important increase in occurrence rate, an unexpected outcome, or a new event that is likely to affect safety of trial volunteers, at the discretion of the Chief Investigator and/or LSM. In addition to the expedited reporting above, the Investigator shall include all SAEs in the annual Development Safety Update Report (DSUR) report.

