9.9 Local Safety Committee

A Local Safety Committee (LSC) will be appointed to provide real-time safety oversight. The LSC will review SAEs deemed possibly, probably or definitely related to study interventions. The LSC will be notified within 24 hours of the Investigators' being aware of their occurrence. The LSC has the power to place the study on hold if deemed necessary following a study intervention-related SAE. At the time of writing the LSC will be chaired by [name], a Clinical Tutor in Medicine, Honorary Consultant Physician and Director, Centre for Tropical Medicine at the University of Oxford. There will be a minimum of two other appropriately qualified committee members. All correspondence between Investigator and LSC will be conveyed by the Investigator to the trial Sponsor.

The chair of the LSC may be contacted for advice and independent review by the Investigator or trial Sponsor in the following situations:

• Following any SAE deemed to be possibly, probably, or definitely related to a study intervention.

• Any other situation where the Investigator or trial Sponsor feels independent advice or review is important.

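### Section 9.5 leaves *possible* out of its definition of an intervention-related AE, while sections 9.2.2, 9.2.5, 9.6.1, 9.9 and 9.10 count it as related

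*Protocol*

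**What the plan says.** Section 9.5 sets out how causality is judged and gives the five-grade scale of Table 5 (0 no relationship, 1 unlikely, 2 possible, 3 probable, 4 definite). It then defines the related category: "An intervention-related AE refers to an AE for which there is a probable or definite relationship to administration of a vaccine". The same section schedules causality assessment for the planned safety reviews, for interim analyses and for the final safety analysis. SAEs are the exception, because the reporting investigator assigns their causality.

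Other sections draw the line one grade lower:

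- 9.2.2, on adverse reactions: "i.e. possibly, probably or definitely related to an IMP) will qualify as adverse reactions".
- 9.2.5, on serious adverse reactions: "believed to be possibly, probably or definitely due to an IMP or any other study treatments".
- 9.6.1, on the local safety monitor, who "will be notified of SAEs that are deemed possibly, probably or definitely related to study interventions".
- 9.9, on the committee's review: "The LSC will review SAEs deemed possibly, probably or definitely related to study interventions".
- 9.10, on the unsolicited-event holding rule, which covers a Grade 3 event "that is considered possibly, probably or definitely related to vaccination", and on the SAE holding rule: "A serious adverse event considered possibly, probably or definitely related to vaccination occurs".

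Section 9.9 also uses the related term without giving its threshold: "The LSC has the power to place the study on hold if deemed necessary following a study intervention-related SAE".

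**The concern.** Two definitions of relatedness are in force, and they differ by exactly one grade of Table 5. An event graded *possible* is an adverse reaction under 9.2.2 but not an intervention-related AE under 9.5. The narrower definition sits in the section that places causality assessment at the safety reviews and the final safety analysis, so an analyst could reasonably take it as the rule for a related-AE summary.

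Two things are at stake. The first is reporting. Section 3.8 presents the study as a bridging study to confirm that changing the production cells has not changed the safety profile, ahead of a phase IIb trial in which 1000 people are to receive the vaccine. A related-AE summary that leaves out *possible* events would sit awkwardly with that purpose, and would not match the events that the causality-based holding rules act on. The second is the reading of 9.9, where the committee reviews SAEs from *possible* upward but its hold power is tied to the term that 9.5 defines more narrowly.

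**Working it through.** The protocol gives no figure to reproduce. The check compares thresholds, followed by one line of arithmetic for scale.

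**Step 1. Thresholds side by side, in Table 5 grades**

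| Place | Use | Grades counted as related |
|---|---|---|
| 9.5 | intervention-related AE | 3–4 |
| 9.2.2 | adverse reaction | 2–4 |
| 9.2.5 | serious adverse reaction | 2–4 |
| 9.6.1 | SAE notification to the safety monitor | 2–4 |
| 9.9 | committee review of SAEs | 2–4 |
| 9.9 | committee hold power | not stated; 3–4 if read with 9.5 |
| 9.10 | holding rules: unsolicited Grade 3 events, life-threatening reactions, SAEs, deaths | 2–4 |
| 9.10 | holding rules: solicited local and systemic events | no causality threshold |

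Section 9.5 is the only place with an explicit threshold of 3–4. No section limits its definition to a particular use or explains the difference.

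**Step 2. What grade 2 contains**

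In Table 5, *possible* requires any one of three criteria joined by *or*: plausible timing, no ready alternative explanation, or resemblance to responses seen with other vaccines. *Probable* requires plausible timing together with one of the other two. *Possible* is therefore the least demanding of the three related grades. The protocol gives no distribution of events over the grades, so how many would fall there is unknown.

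**Step 3. Where the difference can show**

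- Section 5.1.1: the AE outcomes are occurrences of solicited, unsolicited and serious events. None is conditioned on causality, so there is no change under either definition.
- Section 10: safety is described by how often events occur, how severe they are and how long they last. No related-AE table is named, so there is no change to any presentation that the protocol specifies.
- Section 9.5: causality is assessed at the reviews and at the final safety analysis. A related-AE summary prepared there depends on which definition is chosen.
- Section 9.9 against 9.10: for an SAE graded *possible*, 9.10 meets a holding criterion, and 9.9 includes the event in the committee's review. The 9.9 hold power would not reach it if its term carries the 9.5 meaning.

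**Step 4. Scale**

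Input: at most 6 volunteers are vaccinated (section 10). Let k be the number whose highest causality grade is *possible*. Then

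related proportion (grades 2–4) − related proportion (grades 3–4) = k/6.

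For k = 1 this is 1/6 = 16.7 percentage points; for k = 2 it is 2/6 = 33.3 points. The value of k is not known in advance, and these figures show only the size of one step.

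**The case against.** The strongest reply is that the inconsistency changes nothing the protocol has fixed. All AEs are recorded whatever their attribution (9.6), the primary outcomes ignore causality, and the construction of a related-AE table is normally left to the SAP, which is not at hand. A table built on the 9.2.2 term would lose nothing. Notification, committee review and the causality-based holding rules each spell out their own threshold and do not borrow the 9.5 term. Section 9.10 also lets several parties, including the committee, advise a hold for any event that in their judgement endangers volunteers. These points stand, and they rule out several stronger readings that a reader might infer:

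- *The final related-AE tables will drop events.* No such table is specified. The loss occurs only if a summary uses the 9.5 definition.
- *The primary safety result is biased downward.* The primary counts are the same under both definitions.
- *The largest class of related events is removed.* *Possible* has the loosest criteria, but that does not make it the commonest grade. Typical post-vaccination symptoms could well qualify as *probable* through timing and a known pattern.
- *Everything the holding rules act on would be under-reported.* The solicited-event rules use no causality threshold.
- *An SAE graded possible would escape a hold.* Section 9.10 lists it as a holding criterion regardless of 9.5.

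The reply does not remove the contradiction. The protocol states two incompatible definitions rather than leaving one open, so a SAP would have to depart from one of them.

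**Conclusion.** The contradiction is certain on the text: 9.5 counts grades 3–4, and every other explicit causality threshold counts grades 2–4. Its consequence is conditional and limited. If a related-AE summary at a safety review or the final safety analysis follows 9.5, it omits events graded *possible*, at 16.7 percentage points for each volunteer with no higher-graded event. This assumes that such a summary is produced and that all six volunteers form the denominator. Separately, the hold power in 9.9 is ambiguous for an SAE graded *possible*, although other provisions in 9.10 cover such an event. The point should be corrected, but it ranks below an essential fix because no primary outcome, recorded event or listed holding criterion depends on it.

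**What to change.** For reporting, bring the definition in 9.5 into line with 9.2.2, so that *possible*, *probable* and *definite* all count as related, and state that this one definition applies to any related-AE summary. Show the results by causality grade as well, so that a reader who prefers the narrower cut can recover it. Reconcile the wording of 9.5, 9.9 and 9.10 so that the term attached to the committee's hold power has one stated meaning; which meaning governs that power is for the sponsor and the committee to settle.

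The cost is one sentence in 9.5 and a clarification in 9.9. The downside is a slightly higher reported related-AE rate, which the breakdown by grade makes transparent. No data collection, visit or sample size changes.
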